7.5.4 Primary Safety Objective

Demonstrate that the MARVEL 2 features provide pacing as intended.

7.5.4.1 Endpoint Definition

A subject will meet the primary safety endpoint if they are free from the following MARVEL 2 software related events during the entire Holter monitoring period where the MARVEL 2 features are enabled:

1. Pauses lasting longer than two cardiac cycles (where cardiac cycle length is defined by the programmed lower rate interval), AND
2. Episodes of oversensing induced tachycardia exceeding 3-minutes, defined as oversensing accelerometer signal leading to a heart rate exceeding 100 BPM

7.5.4.2 Hypothesis

$H_0: \pi_{AV} \leq 87\%$, versus

$H_a: \pi_{AV} > 87\%$

where π_{AV} is the percentage of subjects meeting the primary safety endpoint during the MARVEL 2 pacing mode.

7.5.4.3 Performance Requirements

The percentage of subjects meeting the primary safety endpoint is significantly greater than 87% (i.e. the lower two-sided 95% confidence interval for the estimate exceeds 87%). For example, in a sample size of 70 subjects with usable Holter datasets, this objective would be met if at least 67 of the 70 subjects (96%) meet the primary safety endpoint. Further, with a sample size of 70 subjects with usable Holter datasets the lower two-sided 95% confidence interval will be 94.9% if all 70 subjects meet the primary safety objective.

7.5.4.4 Analysis Methods

All available Holter recordings (including multiple recordings for subjects evaluated at multiple visits following initial Micra implant) will be used to determine if a subject meets the primary safety endpoint. The ventricular event spreadsheet derived from each Holter file (see section 7.5.2.4) will be used to determine the primary event status associated with each Holter recording. Each ventricular event spreadsheet will be imported into SAS and/or R.

The MARVEL 2 features will be considered enabled when column 6 (F) in the ventricular event spreadsheet has the values 5, 6, 7, or 14.

Next, the ventricular markers from the Micra device will be searched for long intervals. To accomplish this, the programmed lower rate interval will be computed by converting column 3 (C) to seconds by dividing 60 by the value in column 3 (C). Next, the difference in seconds between the current ventricular event and the next ventricular event will be calculated (i.e. the V-V interval). If this value exceeds twice the programmed lower rate interval and there is no telemetry dropout (i.e. column 4 (K) = 0) the event will be flagged for further investigation.

Similarly, the ventricular rate in seconds from one ventricular event to the next will be calculated and used to determine if the rate exceeds 100 bpm (0.6 seconds). If the time from the first ventricular event with a rate exceeding 100 bpm to the last ventricular event with a rate exceeding 100 bpm is greater than 3 minutes, the sequence of events will be marked for further investigation. Note that the ventricular rate associated with ventricular events where there is evidence of telemetry dropout (i.e. column 4 (K) = 1) will not be computed and the ventricular event will be ignored when computing the duration of rates exceeding 100 bpm. This strategy makes the implicit assumption that the higher rate continues through the telemetry dropout period unless the next pair of ventricular events has a rate

below 100 bpm. The telemetry protocol between the implanted Micra and the Holter monitor may result in duplicate ventricular event markers to be transmitted. This would result in multiple entries in the ventricular event spreadsheet with a non-physiological time between the ventricular events. Therefore, ventricular events occurring within 100 ms of a previous ventricular event will be discarded as they are non-physiological (e.g. correspond to a rate exceeding 600 bpm).

For each long interval event identified above, the surface ECG signals and EGM will be manually reviewed to determine if they are true pauses or due to telemetry dropout. For any true pauses, the surface ECG signal, accelerometer signal, and device markers will be examined to determine if the pause was related to the MARVEL 2 algorithm or for another reason (e.g. R-wave undersensing).

Similarly, for each high heart rate event, the surface ECG, the accelerometer signal, and MARVEL 2 markers will be examined to determine if the high heart rates were induced by MARVEL 2 algorithm oversensing or for some other reason (e.g. appropriate rate response, T-wave oversensing). Subjects free from pauses and oversensing induced tachycardia exceeding 3 minutes related to the MARVEL 2 algorithm will be considered to have met the primary safety endpoint.

An exact binomial test will be used to test the primary safety hypothesis. Specifically, the numerator will be the number of subjects meeting the primary safety endpoint. The denominator will be the number of subjects with Holter recordings with usable telemetry while the MARVEL 2 algorithm is downloaded.

[REDACTED]

The following pre-specified subgroups will be evaluated if there are two or more subjects who do not meet the primary safety objective: sex, geography (US versus outside of US), and predominant heart rhythm during Holter recording (normal sinus node function and persistent 3rd degree AV block, intact

AV conduction, or other predominant rhythm). Fisher's exact test will be used to identify differences between subgroups.

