
Inappropriate pacing: Atrial rate tracked to a higher pacing rate
 
The procedure allows steps to temporary set pacing rate to approximately 80 bpm (above the subject's intrinsic rhythm) to collect vector data during parameter settings evaluation
	
Increased risk of symptoms such as: Dizziness, palpitations, heart racing, fatigue, decreased heart rate, shortness of breath, and difficulty sleeping
	
Subjects are under the supervision of an experienced Clinician during the protocol steps
 
The A4 tracking window will typically limit tracking to around 100 bpm. A second, higher A3 threshold is utilized to track above that rate.
 
By using the device's blanking periods, the maximum tracking rate may be programmed to lower than 150 bpm in patients who may be more susceptible to high rate pacing.
 
The algorithm incorporates a tracking-check feature to confirm appropriate tracking above a programmable parameter (off, 90, 100(nominal), 110 bpm). If appropriate tracking is not confirmed, the atrial tracking rate will be limited to less than programmed rate.

Micra device features disabled / modified in MARVEL 2 operation may cause inappropriate pacing: Ventricular Capture Management, Manual Ventricular Capture Management, Rate Response, MRI mode, Sensing assurance.
 
Device Oversensing or Undersensing
 
Unintended Loss of Capture
 
Loss of pacing
	
Increased risk of symptoms such as: Dizziness, palpitations, heart racing, fatigue, decreased heart rate, shortness of breath, and difficulty sleeping
 
If a loss of pacing capture in pacemaker dependent subjects occur, this could cause syncope, decreased heart rate, fainting, asystole, and death
	
Device interrogation prior to software download will be performed. The subject will be monitored in clinic during the study.
 
Activity Mode-Switch will monitor the rate response signal and if the tracking is significantly lower than the activity sensor rate, the device will change to VVIR mode. Clinician will be given the discretion to discontinue MARVEL 2 if subject becomes symptomatic
 
In the case of emergency MRI, MARVEL 2 software can be removed

Skin reaction to adhesive when applying ER220 Holter
	
Increased risk of skin rash/irritation, or allergic reaction
	
Study sites will be trained by Medtronic on applying the ER220 Holter per instructions for use, and will be provided

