17.6.4 Analysis Methods

A Holter monitor will be placed on all study subjects during the MARVEL 2 study procedures. The Holter continuously records ECG and data telemetered from the implanted Micra device. The telemetered data includes ventricular electrograms reflecting ventricular activation and marker channel. The marker channel includes the ventricular sensed and paced event markers as well as markers unique to the MARVEL 2 features including whether the MARVEL 2 features sense an atrial beat (A4 signal). In addition, the Holter records supplemental marker data including V-V interval, pacing rate, pacing mode, pacing amplitude, pacing pulse width, R-wave amplitude, and sensor counts.

Each Holter dataset will be reviewed by Medtronic personnel experienced in the review of Holter recordings to determine the recording time, quality of the recording, and confirm correct MARVEL 2 feature operation. Holter datasets will be further analyzed manually and using programmed scripts to extract information related to:

- Ventricular sensing (including V-V interval)
- A4 detection

All available Holter recordings (including multiple recordings for subjects evaluated at multiple visits following initial Micra implant) will be used to determine if a subject meets the primary safety endpoint. First, the ventricular markers from the Micra device will be searched for long intervals. For each of these identified long intervals, the surface ECG signal will be manually reviewed to determine if they are true pauses or due to telemetry dropout. For any true pauses, the surface ECG signal, accelerometer signal, and device markers will be examined to determine if the pause was related to the MARVEL 2 algorithm or for another reason (e.g. T-wave oversensing). To identify any potential oversensing induced tachycardia the ventricular markers from the Micra will be searched for indication of a heart rate above 100 BPM exceeding 3 minutes. If high heart rates exceeding this criterion are identified, the surface ECG, the accelerometer signal, and MARVEL 2 markers will be examined to determine if the high heart rates were due to MARVEL 2 algorithm oversensing. Subjects free from pauses and oversensing induced tachycardia exceeding 3 minutes related to the MARVEL 2 algorithm will be considered to have met the primary safety endpoint.

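### The primary safety pause screen searches device markers only, so a pause from consecutive non-captured paces would never reach ECG review

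*SAP*

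**What the plan says.** The primary safety endpoint (SAP 7.5.4.1, Protocol 8.2.1.2) counts only events related to the MARVEL 2 software. Its first component is "Pauses lasting longer than two cardiac cycles (where cardiac cycle length is defined by the programmed lower rate interval), AND" and its second is oversensing-induced tachycardia.

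Both documents find pauses in the same order. Protocol 17.6.4: "First, the ventricular markers from the Micra device will be searched for long intervals". SAP 7.5.4.4: "Next, the ventricular markers from the Micra device will be searched for long intervals". The SAP then computes the time from each ventricular marker to the next and applies this rule: "If this value exceeds twice the programmed lower rate interval and there is no telemetry dropout", the event is flagged. Waveform review then follows for the flagged set: "For each long interval event identified above, the surface ECG signals and EGM will be manually reviewed to determine if they are true pauses" or telemetry dropout. A true pause is finally judged to be algorithm-related or not.

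Protocol 17.5.5 explains what a ventricular marker is: it records that the device sensed a ventricular event or delivered a pace.

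One row of Protocol Table 4 (section 14.1) deals with Micra functions that MARVEL 2 operation disables or modifies, including Ventricular Capture Management. The same row lists "Unintended Loss of Capture" and gives the possible harm: "If a loss of pacing capture in pacemaker dependent subjects occur, this could cause syncope, decreased heart rate, fainting, asystole, and death".

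**The concern.** A marker is the device's own account of what it did or sensed. If paces fail to capture, pace markers continue on schedule while the ventricle is silent. The marker search sees ordinary intervals, raises no flag, and the ECG is not opened. The manual review cannot correct this, because it begins only after a flag.

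The endpoint is meant to show adequate rate support (Protocol 8.2.1.2). Loss of capture is one way in which rate support fails, and the risk table names it. An endpoint that cannot register it gives less assurance than it appears to. The error also runs one way: a missed software-related pause turns a failing subject into an event-free one and never the reverse.

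The efficacy analysis takes the opposite approach. Protocol 17.5.4 keeps device markers out of P-wave identification and has each P-wave checked by a human reader. Finding pauses has no such independence from the device.

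**Working it through.** **The plan's own figures first.** Inputs from SAP 7.5.4.3 and 7.5.4.5: n = 70, performance goal 87%, one-sided alpha 0.025, assumed true rate 98%, success at 67 or more event-free.

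- The exact (Clopper-Pearson) lower limit is the 0.025 quantile of Beta(x, n − x + 1). For x = 66 it is 86.0% (fails), for x = 67 it is 88.0% (passes), and for x = 70 it is 0.025^(1/70) = 94.9%.
- P(X ≥ 67 | 70, 0.87) = 0.0145 and P(X ≥ 66 | 70, 0.87) = 0.041, so 67 is the smallest passing count.
- P(X ≥ 67 | 70, 0.98) = 0.948, which agrees with the stated power of at least 90%.

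The stated sample size, limits and power all reproduce. The issue is which pauses can enter the count.

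**Marker interval against true interval.** Let the lower rate be LR, the pacing rate r, and k the number of consecutive non-captured paces with no escape beat.

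- Marker V-V = 60/r
- True R-R = (k + 1) × 60/r
- Flag limit = 2 × 60/LR

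Take LR = 50 bpm, which Protocol 13.7.12 gives for auto-setup and which is assumed here for the rest of the recording. The limit is 2 × 1.2 = 2.4 s.

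| r (bpm) | k | Marker V-V (s) | True R-R (s) | True pause? | Flagged? |
|---|---|---|---|---|---|
| 50 | 1 | 1.2 | 2.4 | no (equals the limit) | no |
| 50 | 2 | 1.2 | 3.6 | yes | no |
| 50 | 3 | 1.2 | 4.8 | yes | no |
| 70 | 2 | 0.857 | 2.57 | yes | no |
| 80 | 2 | 0.75 | 2.25 | no | no |
| 80 | 3 | 0.75 | 3.0 | yes | no |

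At LR = 60 bpm with pacing at 60 bpm, two lost captures give R-R 3.0 s against a 2.0 s limit, again with no flag. At least two consecutive losses are needed when pacing at the lower rate, and more at faster rates.

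**Control case.** If no pace is delivered and no marker appears for 2.8 s, the marker interval is 2.8 s, above 2.4 s, and the screen flags it. The screen works for absent output. It is blind only when markers continue.

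**Oversensing that inhibits pacing.** Suppose two false ventricular senses follow a true beat at 0.8 s spacing (assumed), and pacing resumes 1.2 s after the second. True R-R = 0.8 + 0.8 + 1.2 = 2.8 s, the longest marker gap is 1.2 s, and nothing is flagged.

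**Effect on the test.** The documents give no frequency for such pauses. At n = 70, one missed subject changes the result only if 66 subjects are truly event-free and 67 are counted. An observed 70/70 would need four missed subjects (70 − 4 = 66). As an assumed range, let m be the share of truly failing subjects whose pauses are all invisible to the marker search. At a true rate of 87%, the apparent rate is 1 − 0.13 × (1 − m), and the chance of declaring success is:

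- m = 0: 0.0145
- m = 10% (apparent rate 88.3%): 0.030
- m = 25% (90.25%): 0.080
- m = 50% (93.5%): 0.325

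These values show how the rule responds. They do not estimate m.

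**The case against.** The strongest reply is that other review exists. The synopsis says all Holter recordings will be evaluated for pauses. Protocol 17.6.4 and SAP 7.5.1 have experienced staff review every dataset for correct feature operation, subjects are monitored in clinic, and all adverse events and device deficiencies are collected. A symptomatic pause would probably come to light. This stands as protection for safety reporting, but not for the endpoint: none of these routes is tied to scoring. Where Protocol 17.6.4 lists what the manual and scripted analysis extracts, it names ventricular sensing and A4 detection, not capture.

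Redaction is a fair caution. SAP 7.5.2, where the ventricular event spreadsheet is derived, is blacked out and could contain an ECG step. The readable Protocol 17.6.4 describes the procedure without one.

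A reader might infer more than the documents support:

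- *That ventricular oversensing is equally a gap.* Table 4 names device oversensing without a chamber. Oversensing also shortens marker intervals, and if the marker rate stays above 100 bpm for more than 3 minutes the tachycardia review is triggered. Protocol 17.6.4 gives T-wave oversensing as an example of a cause other than the algorithm, so some such pauses would not count even if found.
- *That loss of pacing is missed too.* With no pulse and no marker, the existing search flags the gap.
- *That Table 4 says loss of capture results from changing capture management.* The two share a row. The causal link is plausible but not stated.
- *That every confirmed capture or sensing pause should be a failure.* That would replace the relatedness decision and redefine an endpoint limited to software-related events.

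**Conclusion.** The point holds for loss of capture. On the readable text, a pause made of consecutive non-captured paces cannot be flagged, is not reviewed, and leaves the subject event-free. It holds more weakly for oversensing that inhibits pacing, which can be missed in the same way but may be judged unrelated.

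The conclusion assumes no escape beat during the run, at least two consecutive losses (more when pacing runs above the lower rate), and no ECG-based search in the redacted SAP text. The timings at 50 bpm also assume that the auto-setup lower rate applies elsewhere.

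The direction of bias is certain for related events, but its size is unknown. The documents do not show that such pauses will occur, that the type I error is inflated by any particular amount, or that a passing result would be wrong. The 86.0% and 88.0% limits show only what one missed subject does at the boundary. The change is still worth making: the signals are already recorded, and it removes an error that can only favour the sponsor.

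**What to change.** In SAP 7.5.4.4, add an automated screen on the surface ECG (or electrogram) that flags every QRS-to-QRS interval longer than twice the programmed lower rate interval while the MARVEL 2 features are enabled, whatever the marker spacing. Send these intervals to the manual review that already exists for marker-flagged intervals.

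Keep the case-by-case relatedness decision for endpoint scoring, so the endpoint definition does not change. Report all confirmed pauses by cause, including loss of capture and sensing failure, and include those judged unrelated so that readers can see what was set aside.

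If the redacted SAP text already contains such a step, a cross-reference from 7.5.4.4 is enough.

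The cost is SAP wording, one QRS-detection pass over recordings already made, and manual rejection of false flags from ECG artefact. No new data collection is needed, and the sample size and decision rule stay as they are.

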17.5.5 Determination of Subjects and Data for Analysis

All subjects with normal sinus node function and persistent 3rd degree AV block during Holter monitoring with at least 500 evaluable beats during VVI pacing and at least 500 evaluable beats during MARVEL 2 adaptive pacing in which the device is providing VDD pacing¹ will be included in the primary analysis for this objective. For *de novo* subjects, only data collected during the 20-minute resting period at pre-hospital discharge will contribute to the analysis of the primary objective. (Note that ancillary objective number five will compare the atrioventricular synchronous pacing rates observed at pre-hospital discharge and at 1-month post-implant.) However, if a *de novo* subject does not have usable Holter data at pre-hospital discharge, their Holter data approximately 1-month post-implant will be used in the analysis, if available.

¹ Cardiac cycles during MARVEL 2 adaptive mode pacing that occur during an AV conduction test will not be considered evaluable as the pacing mode is set temporarily to VVI40 while the device checks for intrinsic AV conduction.

Loss of communication between the Holter and the implanted Micra device, called telemetry dropout, can lead to loss of the marker indicating a ventricular event was sensed or a ventricular pace was delivered. Therefore, beats with no ventricular sense or pace markers and indication of telemetry dropout in the first 300 ms after a P-wave will be discarded (i.e. they are not evaluable beats).

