17.6.6 Missing Data and Sensitivity Analyses

The primary source of missing data for this objective is anticipated to be Holter usability status and telemetry dropout during MARVEL adaptive mode pacing. Note that both sources of missing data can plausibly be assumed independent of primary safety endpoint status as Holter usability status is primarily related to electrode contact. However, to quantify the amount of missing data, the number of unusable Holter files and the proportion of beats during MARVEL 2 adaptive pacing with telemetry dropout will be computed.

If the level of missing data is an issue, tipping point methodology will be employed to evaluate the sensitivity of the statistical inference to the missing data. Additionally, stochastic methods may be employed to aid in interpreting the likelihood the tipping point would be met or exceeded.

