7.5.4.7 Missing Data and Sensitivity Analyses

The primary source of missing data for this objective is anticipated to be Holter usability status and telemetry dropout during MARVEL adaptive mode pacing. Note that both sources of missing data can plausibly be assumed independent of primary safety endpoint status as Holter usability status is primarily related to electrode contact. However, to quantify the amount of missing data, the number of unusable Holter files and the proportion of beats during MARVEL 2 operation with telemetry dropout will be computed.

If Holter data from subjects who had the MARVEL 2 software downloaded is missing (e.g. deemed entirely unusable, Holter never placed on subject), it will be included in a tipping point analysis to determine the sensitivity of the statistical inference to the missing data. If the tipping point is less than the number of subjects with missing data, stochastic methods may be employed to aid in interpreting the likelihood the tipping would be achieved. Specifically, simulations from a Beta distribution with shape parameters based on the observed data will be used to compute the predictive probability of observing or exceeding the tipping point.

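### In the readable text, the SAP's pause screen drops long V-V intervals marked as telemetry dropout, which the protocol would settle by surface-ECG review, so a true pause there can be scored as event-free.

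*SAP*

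**What the plan says.** **Protocol 17.6.4.** The ventricular markers are searched for long intervals, with no condition on dropout. Then: "For each of these identified long intervals, the surface ECG signal will be manually reviewed to determine if they are true pauses" or the result of dropout. The same section notes: "The Holter continuously records ECG and data telemetered from the implanted Micra device".

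**Protocol 17.5.5** explains the term: "Loss of communication between the Holter and the implanted Micra device, called telemetry dropout, can lead to loss of the marker" of a ventricular sense or pace.

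**SAP 7.5.4.4, pauses.** The V-V interval is computed from the ventricular event spreadsheet. If that interval "exceeds twice the programmed lower rate interval and there is no telemetry dropout (i.e. column 4 (K) = 0) the event will be flagged". The review step then covers only what has been flagged: "For each long interval event identified above, the surface ECG signals and EGM will be manually reviewed". Subjects with no confirmed software-related event are scored as meeting the endpoint.

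**SAP 7.5.4.4, tachycardia.** No rate is computed for dropout-marked events, and they are ignored when the duration of a high-rate run is measured. The SAP adds: "This strategy makes the implicit assumption that the higher rate continues through the telemetry dropout period", unless the next pair of events shows a rate below 100 bpm.

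**Missing data.** Protocol 17.6.6 and SAP 7.5.4.7 both name telemetry dropout as a main source of missing data for this objective. Both argue that it is plausibly independent of safety status, and both commit to reporting its extent. Protocol 17.6.6 adds: "If the level of missing data is an issue, tipping point methodology will be employed to evaluate the sensitivity of the statistical inference". SAP 7.5.4.7 words its tipping-point scope for missing Holter data as "e.g. deemed entirely unusable, Holter never placed on subject), it will be included in a tipping point analysis".

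**The concern.** The protocol uses the ECG to decide whether a long interval is a pause or dropout. The SAP lets the dropout marker decide first and gives the reviewers only the remainder. Yet the SAP's review step still describes its task as separating true pauses from dropout, a question its own filter has largely answered already.

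A dropout mark does not show that the ventricle was paced. It shows that communication between device and Holter was lost. Because surface ECG is recorded as well as telemetered data, a pause may still be visible on the ECG when the markers are missing.

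The error runs in one direction. A subject whose only qualifying event is a pause in a dropout-marked interval stays in the denominator and is added to the numerator as a success. Study success requires rejecting the safety null hypothesis, so this endpoint should not depend on a filter that can only help it.

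**Working it through.** **1. Trace one interval through both documents.** Take a V-V gap longer than twice the programmed lower rate interval, marked as dropout, with a real software-related pause inside it.

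| Step | Protocol 17.6.4 | SAP 7.5.4.4 (readable text) |
|---|---|---|
| Screen | Found as a long interval | Not flagged, because the dropout condition fails |
| Surface-ECG review | Yes | No, since only flagged intervals are reviewed |
| Outcome | Judged a pause if the ECG shows one, then assessed for cause | No event recorded |
| Subject's score | Can fail | Meets the endpoint if there is no other event |

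**2. Compare the two SAP screens.** Neither uses a dropout-marked interval as evidence in itself. The tachycardia screen bridges a gap when high rates are seen on both sides. The pause screen has no equivalent step.

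**3. Reproduce the plan's safety figures.** Inputs from SAP 7.5.4.3 and 7.5.4.5: n = 70, goal 87%, one-sided alpha 0.025, success at 67 or more, planned rate 98%.
- Exact lower 95% limits: 67/70 gives 88.0%, 66/70 gives 86.0% and 70/70 gives 94.9%.
- P(X ≥ 67 | n = 70, p = 0.87) = 0.0145. With a cut-off of 66 it would be 0.041, so 67 is correct.
- P(X ≥ 67 | n = 70, p = 0.98) = 0.948, consistent with the stated power of at least 90%.

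**4. Illustrate the effect of missed events.** Let m be the share of event subjects scored as event-free because every qualifying pause is dropout-marked and there is no qualifying tachycardia. The documents give no value, so m is an assumption. With true event-free rate p, the scored rate is 1 − (1 − p)(1 − m).

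| m | Scored rate at p = 0.87 | P(X ≥ 67 of 70) | Scored rate at p = 0.98 | P(X ≥ 67 of 70) |
|---|---|---|---|---|
| 0 | 0.8700 | 0.0145 | 0.980 | 0.948 |
| 0.05 | 1 − 0.13 × 0.95 = 0.8765 | 0.021 | 1 − 0.02 × 0.95 = 0.981 | 0.956 |
| 0.10 | 1 − 0.13 × 0.90 = 0.8830 | 0.030 | 1 − 0.02 × 0.90 = 0.982 | 0.962 |

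**5. Check whether a threshold for m is meaningful.** The m at which false success passes 0.025 is about 7.6% at n = 70, 13.5% at n = 75, 0.5% at n = 76, 9.7% at n = 96 and 3.1% at n = 100. At each n the cut-off is the smallest count with exact error at or below 0.025. The values jump because the binomial test is discrete, so no single one is a tolerance limit.

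**6. Check the field reference.** The filter cites column 4 (K). Elsewhere the SAP pairs 3 with C and 6 with F (7.5.4.4) and 11 with K (7.5.3.4). The number and the letter therefore do not match.

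**The case against.** The strongest objection is that the filter depends on how the dropout marker is built. That belongs to SAP 7.5.2.4, which is redacted, as is part of 7.5.4.4. If the marker is set only after the ECG is checked, the gap may vanish. This stands as a limit on the finding, although nothing readable says it is so.

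Second, the plan treats dropout openly as missing data, argues independence and reports its proportion, which gives a reader some basis for judging the likely size. SAP 7.5.1 also has each Holter dataset reviewed for quality and correct feature operation. Both are real safeguards, but neither sends these intervals to pause review. Independence makes bias less likely to be large. It does not stop a pause inside a dropout interval from being counted as a success.

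Third, a reader might infer that the SAP is cautious about dropout for tachycardia and takes the opposite line for pauses. The text does not support that: a tachycardia lying wholly within dropout would also be missed, and a single long interval has nothing to bridge. The difference is only that one screen bridges gaps and the other has no counterpart.

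Fourth, the 87% illustration needs 13% of subjects to have events, whereas the plan expects more than 98% event-free and reports no such events in the predecessor study. That is fair, and it is why the effect is probably small.

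Finally, some pauses confirmed on ECG could not be attributed, because the accelerometer signal and markers are telemetered too. This is true. Those subjects would then be recorded as missing rather than as successes.

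**Conclusion.** The concern holds in the readable text. The SAP narrows a review that the protocol applies to every long interval, and the narrowing can only favour success on a co-primary safety endpoint. It should be corrected before analysis.

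The size is unknown. Under assumed missed shares of 5% and 10%, false success at n = 70 rises from 0.0145 to 0.021 and 0.030 at the 87% boundary. At the planned 98% rate, the pass probability rises by 0.8 or 1.4 percentage points (0.948 to 0.956 or 0.962).

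A reader might infer that type I error is lost once some fixed share of events is hidden, or that the safety conclusion is unreliable. The documents support neither: they give no dropout or pause rate, and the crossing point moves sharply with n. Confidence is medium, because a compensating step may lie in the redacted text. The mismatch in column 4 (K) is a separate labelling point and does not bear on the finding.

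**What to change.** - In SAP 7.5.4.4, remove the no-dropout condition from the pause flag, so that every V-V interval longer than twice the lower rate interval goes to surface-ECG review, as in protocol 17.6.4. If a redacted step already does this, refer to it in 7.5.4.4.
- Report how many dropout-marked long intervals were reviewed and how many were confirmed as pauses.
- In the SAP 7.5.4.7 tipping-point analysis, include as missing any otherwise event-free subject with such an interval that is unreadable on ECG, or with a confirmed pause that cannot be attributed. State in advance how that subject is scored in the main exact test.
- Check and correct the column 4 (K) reference.

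The cost is SAP wording, code and more intervals for the same reviewers. Many will be dropout artefacts, and the volume cannot be forecast without a dropout rate. The sample size, the cut-off and the test do not change, and the protocol already plans this review.
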